6.1.3 Adverse Device Effect (ADE)

An ADE is an adverse event related to the use of an investigational medical device. This definition includes adverse events resulting from insufficient or inadequate instructions for use, deployment, implantation, installation, or operation, or any malfunction of the investigational medical device. This definition includes any event resulting from use error or from intentional misuse of the investigational medical device. *Any adverse event which the clinical investigator believes has even a possible relationship to the device will be classified as an ADE.*

6.1.4 Serious Adverse Device Effect (SADE)

An SADE is an adverse device effect that has resulted in any of the consequences characteristic of a serious adverse event.

6.1.5 Unanticipated Serious Adverse Device Effect (USADE)

An USADE is a serious adverse device effect which by its nature, incidence, severity or outcome has not been identified in the current version of the risk analysis report.

6.1.6 Anticipated Serious Adverse Device Effect (ASADE)

An ASADE is a serious adverse device effect which by its nature, incidence, severity or outcome

has been identified in the risk analysis report.

Table 2: Summary of the classification for adverse	events
--	--------

Adverse Events	Non-Device Related	Device Related						
Non-serious	Adverse Event (AE)	Adverse Device Effect (ADE)						
		Serious Adverse Device Effect (SADE)						
Serious	Serious Adverse Event (SAE)	Anticipated	Unanticipated					
		Anticipated Serious Adverse Device Effect (ASADE)	Unanticipated Serious Adverse Device Effect (USADE)					

6.2 Assessment of Adverse Events

In the event of an adverse event, the investigator or another suitably qualified clinician who is trained in recording and reporting AEs and have been delegated to this role (such delegation must be captured in the study site delegation log) must review all documentation (e.g., hospital notes, laboratory and diagnostic reports) relevant to the event. Each adverse event should be assessed for seriousness, relationship to the study device or the procedure, severity, outcome, and expectedness, as described below, by the Investigator.

6.2.1 Seriousness

An adverse event will be described as serious if it meets the definition in Section 6.1.2. The rationale for the assessment shall be provided in a short narrative.

6.2.2 Relationship to the Study Device

The investigator should assess the relationship of the adverse event to the implanted product (e.g., TN-SM device and dental implant) and provide the rationale in a short narrative. The relationship should be assessed using the following categories:

- Definitely related There is a reasonable causal and temporal relationship between the treatment with the study device and the adverse event.
- Possibly related The causal and temporal relationship between the treatment with the study

device and the adverse event is less likely; however, the determination that there is no relationship cannot be made.

 Not related – A causal relationship with device application can be definitely excluded. By definition, all AEs/ADEs, with a start date before the surgery procedure at Visit 2 must be assigned a "not related" relationship with study device.

NOTE: Device deficiencies that might have led to an SAE are always related to the medical device.

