	Restorative Records	6	Health Check, Records for Fabrication of Definitive Restoration (Impressions or scans, shade, jaw relation, etc.), Photographs	3-weeks post implant uncovering			
	Insertion of Definitive Restoration (Baseline)	7	Insertion of Definitive Restoration, Health Check, Satisfaction Survey, Periodontal & Peri-Implant Measurements, Radiographs, Photographs	4 - 6 months post TN-SM device and implant placement			
	3-month Follow-up	8	Health check, Satisfaction Survey, Periodontal & Peri-Implant Measurements, Radiographs, Photographs, Implant Success	3-months post- functional loading			
	6-month Follow-up – Primary Endpoint	9	Health Check, Satisfaction Survey, Periodontal & Peri-Implant Measurements, Radiographs, Photographs, Implant Success	6-months post- functional loading			
	9-month Follow-up	9.5	Health Check, Satisfaction Survey, Periodontal & Peri-Implant Measurements, Radiographs, Photographs, Implant Success	9-months post- functional loading			

Protocol DVAL18041 Version 3.0

	12-Month Follow-up	10	Health check, Satisfaction Survey, Periodontal & Peri-Implant Measurements, Radiographs, Photographs, Implant Success	12-months post- functional loading				
	15-month Follow-up	11	Health Check, Satisfaction Survey, Periodontal & Peri-Implant Measurements, Radiographs, Photographs, Implant Success	15-month post- functional loading				
	18-month Follow-up	12	Health Check, Satisfaction Survey, Periodontal & Peri-Implant Measurements, Radiographs, Photographs, Implant Success	18-month post- functional loading				
	21-month Follow-up	13	Health Check, Satisfaction Survey, Periodontal & Peri-Implant Measurements, Radiographs, Photographs, Implant Success	21-month post- functional loading				
	24-month Follow-up	14	Health Check, Satisfaction Survey, Periodontal & Peri-Implant Measurements, Radiographs, Photographs, Implant Success	24-month post- functional loading				
Study Products:	Commercially a	Tetranite Stabilization Material, TN-SM Commercially available endosseous dental implants Manufacturer's recommended prosthetic components for the implant systems						
Registration Status:	TN-SM is the e	TN-SM is the experimental device under study.						

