4.1.2 Dental Implants and Restorative Components

The study clinician may select the appropriate dental implants, abutments and other restorative components from any legally marketed components that are labeled as compatible. The prostheses fabricated for the study subjects will be single crowns.

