6.2.3 Relationship to the Procedure

The investigator should assess the relationship of the adverse event to the implant procedure (e.g. placement of TN-SM device and the dental implant) and provide the rationale in a short narrative. The relationship should be assessed using the categories described in Section 6.2.2.

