7.3 Analysis of Safety Endpoints

For analysis of safety endpoints, summary tables and/or listings will be provided for all adverse events by event category. Adverse events will also be summarized by relationship to the study device, implant procedure, by seriousness, severity and by outcome. Adverse events leading to discontinuation from the study will be tabulated. Except where indicated, a subject reporting the same adverse event more than once will be counted once when calculating the number and percentage of subjects with that particular event. Except where indicated, if a subject reports the same adverse event more than once, the strongest relationship to the procedure and/or device recorded for the event will be presented.

Adverse events that occurred in screen failure subjects will be presented separately.

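### The device-relationship rating for adverse events does not say consistently whether it covers TN-SM alone or TN-SM plus the marketed implant, so the planned device-related AE summary is ambiguous

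*Combined protocol and SAP*

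**What the plan says.** The Synopsis (Registration Status) states that "TN-SM is the experimental device under study", and Section 4.1.1, which describes the study device, describes TN-SM. The implant is not investigational: under Section 4.1.2 the clinician "may select the appropriate dental implants, abutments and other restorative components from any legally marketed components".

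Section 6.2.2 tells the investigator to rate how each adverse event relates to the "implanted product (e.g., TN-SM device and dental implant"). The categories that follow use a different object. The highest one reads: "There is a reasonable causal and temporal relationship between the treatment with the study device and the adverse event". Section 6.2.3 asks for a second rating, against the "implant procedure (e.g. placement of TN-SM device and the dental implant"), on the same scale. No section asks for a rating against the dental implant on its own.

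Section 7.3 then plans: "Adverse events will also be summarized by relationship to the study device, implant procedure, by seriousness, severity and by outcome". The first secondary endpoint (Synopsis and Section 2.2.1) is the incidence, severity and duration of device-related or device-attributed events. Section 3.5 fixes 20 subjects and no controls.

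**The concern.** The first secondary endpoint depends on attribution to the device, and there is no comparison group from which a background rate of implant complications could be read. The recorded relationship therefore carries much of the weight. If that field covers the adhesive and the implant together, an ordinary complication of a marketed implant can enter the table as device-related. If some investigators follow the lead sentence of Section 6.2.2 and others follow its categories, the table mixes two definitions and nothing in the data shows which was used.

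The classification also matters beyond one table. ADE status feeds the reporting rules in Sections 6.3.4 and 6.3.5, and an excessive incidence of known ADEs is one of the grounds for early termination in Section 9.4. Sections 2 and 3.1 say the pilot is meant to test measures and procedures for a larger study, so this is the natural point to settle the measure.

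**Working it through.** The plan gives no figure to reproduce: the sample size is 2 × 10 = 20 by decision, and all analyses are descriptive. The check is a comparison of the texts, followed by a labelled illustration.

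**What each place takes as the object of the rating**

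| Place | Object |
|---|---|
| Synopsis; 4.1.1 | TN-SM alone |
| 6.1.3 (ADE definition) | An investigational medical device, hence TN-SM |
| 6.2.2, heading and categories | The study device |
| 6.2.2, instruction | TN-SM and dental implant together |
| 6.2.3, instruction | Placement of TN-SM and of the implant together |
| 7.3, tabulation | Study device; implant procedure |

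The instruction in 6.2.2 disagrees with its own heading and categories and with 6.1.3. The procedure rating cannot be used to subtract the implant, because it pools the two placements. So neither tabulated rating is specific to TN-SM under the wording of the instructions.

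**Rules that push borderline events upward.** A rating of not related requires causation to be definitely excluded (6.2.2). A possible relationship is enough for an ADE (6.1.3). For a repeated event the strongest recorded relationship is shown (7.3). An implant failure requiring removal is an SAE (6.1.2), so a pooled rating of at least possible can make it a SADE.

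**Size of the ambiguity.** One subject is 1/20 = 5 percentage points overall, or 1/10 = 10 points within a center. The documents give no numeric rate of implant-only complications, so let p be an assumed proportion of subjects with such an event. Suppose that TN-SM itself causes none, that subjects are independent, and that every such event is rated at least possibly related wherever the pooled reading is used. With m subjects rated on the pooled reading, the expected number counted as device-related is m × p, and the chance of at least one is 1 − (1 − p)^m.

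| Assumed p | Both centers pooled (m = 20): expected; P(≥1) | One center pooled (m = 10): expected; P(≥1) | Neither (m = 0) |
|---|---|---|---|
| 2% | 0.4; 33% | 0.2; 18% | 0 |
| 5% | 1.0; 64% | 0.5; 40% | 0 |
| 10% | 2.0; 88% | 1.0; 65% | 0 |
| 20% | 4.0; 99% | 2.0; 89% | 0 |

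For p = 10%: 20 × 0.10 = 2 and 1 − 0.9^20 = 0.88; 10 × 0.10 = 1 and 1 − 0.9^10 = 0.65. The spread across a row comes from the reading of 6.2.2 alone, with no difference in what happened to the subjects. Because every implant-only event is assumed to be rated related, the entries are upper values for the chosen p.

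**A second mismatch in the same section.** Section 6.2.2 makes all events starting before surgery not related and places that surgery at Visit 2. Table 1 and Section 5.3 place surgery at Visit 3. The status of an event starting between those visits is therefore unclear.

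**The case against.** The strongest reply is that a reader might infer more than the text supports. It is tempting to say that every event due only to the implant will be counted as device-related. The documents do not establish that: the categories in 6.2.2 and the ADE definition point to the study or investigational device, and an investigator who follows them could rate an implant-only event as not related. Nor do 6.2.2 and 6.2.3 mention the crown, so nothing there says that prosthetic events are pooled in. This stands, and it is why the defect is ambiguity and not a uniform miscount.

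It is also tempting to say that attribution to TN-SM is impossible and that the relationship field is the sole means to it. That goes too far. Each rating needs a short written rationale (6.2.2, 6.2.3). An independent committee adjudicates SAEs (6.4), which by rule include failures requiring implant removal. Device deficiencies have their own reporting route (6.3.3), bone loss flagged by the central radiologist is reviewed case by case (6.3.4), and stabilization failures are logged (5.3.4, 5.5). With 20 subjects these can be read one at a time. They do not, however, supply a TN-SM-specific relationship variable or a planned table, and adjudication is limited to SAEs.

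Two further points stand. Over-attribution is the cautious direction for a first safety summary, and TN-SM and the implant are placed in one procedure, so any split is partly judgement. In addition, Section 2.2.1 speaks of systemic effects and events while the Synopsis does not, so the weight of local implant events in the endpoint is itself unclear.

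**Conclusion.** The point holds as an inconsistency that leaves the planned device-related AE summary ambiguous. On the wording of the instruction it may include events due only to the marketed implant. On the wording of the categories and the ADE definition it should not. Centers can reasonably differ. The error is mainly toward over-attribution to TN-SM, at 5 percentage points per subject affected.

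How many subjects would be affected is not known from the documents. The figures of 0 to 4 subjects depend on assumed rates of 2% to 20% and on every implant-only event being rated related. A reader might instead take the small share of Table 3 entries that name TN-SM as a measure of misattribution. It is not one: entries in a list are not event frequencies, expectedness is judged only after an event is rated as related, and entries such as loosening or mobility may reflect failure of TN-SM itself.

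The conclusion assumes that the AE case report form, which is not in the documents, follows Sections 6.2.2 and 6.2.3. This is a cheap improvement that should be made. It does not undermine the study.

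**What to change.** 1. Define the study device once, as TN-SM, and use that term in the same sense in 6.1.3, 6.2.2, 6.2.3 and 7.3.
2. In 6.2.2 and 6.2.3 record three relationship ratings per event: TN-SM; dental implant or prosthesis; procedure. Keep the existing three-level scale.
3. Base ADE and SADE classification on the TN-SM rating (possible or definite), which agrees with the definition already in 6.1.3.
4. In 7.3 tabulate by the TN-SM rating first, and keep the combined TN-SM-or-implant table as the conservative view.
5. Reconcile the reference in 6.2.2 to surgery at Visit 2 with Table 1 and Section 5.3, which place it at Visit 3.

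The cost is one or two added data fields, one extra table and a short addition to site training. The limit is that the split remains partly investigator judgement: in a single-arm study it makes the endpoint interpretable as recorded attribution to TN-SM, not as a comparison. That is the reason to keep the combined table beside it.

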6.2.3 Relationship to the Procedure

The investigator should assess the relationship of the adverse event to the implant procedure (e.g. placement of TN-SM device and the dental implant) and provide the rationale in a short narrative. The relationship should be assessed using the categories described in Section 6.2.2.

6.2.4 Severity

Each adverse event should be assessed by the investigator for its severity, or the intensity of an event experienced by a subject, using the following:

- Mild discomfort noticed, but no disruption in daily activities; the event is easily tolerated by the subject
- Moderate discomfort severe enough to reduce or affect normal daily activity
- Severe Inability to work or perform normal daily activity and/or the subject's life is at risk from the adverse event

The maximum severity observed is to be recorded, except if there is a significant worsening in an AE/ADE severity after device intake, then the change will be tracked as a new AE/ADE record as follows:

- The same wording describing the original AE/ADE must be used.
- Outcome of the initial entry should be designated as 'worsened'.
- The end date of the previous AE/ADE must equal the start date of the new AE/ADE.

6.2.5 Outcome

The outcome should reflect the status of the adverse event at the time of recording.

- Resolved The subject fully recovered from the event without any sequelae. This option also applies when it is unknown whether there are sequelae.
- Resolved with sequelae The subject's condition stabilized despite the persistence of sequelae (e.g., lesion or medical condition which is a consequence of the event). This option does not

apply to irreversible congenital anomalies (see under "ongoing").

- Ongoing The subject has not yet recovered from the event. By convention, in the case of an irreversible congenital anomaly, the "Ongoing" option should be chosen and understood as "Not recovered/Not resolved". The same applies to conditions that are not yet resolved, but are controlled by medication (e.g., diabetes, epilepsy) and therefore may not have any symptoms.
- Worsened The severity of the AE/ADE increased.
- Fatal The event is related to a death; whether it caused death or contributed to it. If the subject died of a different cause, prior to resolution of the AE/ADE, the outcome of this AE/ADE should be designated "Ongoing", and not "Fatal", and an end date should not be specified.
- Unknown Knowledge of the current status of the AE/ADE is truly not available to the investigator (i.e. event was ongoing at last observation, but no further contact with the subject could be established). However, all efforts should be made to determine the outcome of any AE, especially that of an SAE/SADE.

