3.5 Study Sample Size

This study size will enroll 20 subjects, 10 at each of the two Research Centers. The enrollment will be capped at 20 subjects total and will not include control subjects.

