7.4.4 Missing Data

Every effort will be made to minimize the amount of missing data. If a subject drops out of the study prior to completing their primary endpoint assessment, every effort will be made to measure their primary endpoint immediately prior to discontinuation if possible. No missing data will be imputed.

8 Data Management

The general data management procedures are described below, details can be found in the Data Management Plan. Required clinical data for this study will be collected and recorded in the clinical database using an electronic case report form for all study subjects from whom informed consent is obtained. Research Center numbers and subject numbers will be used to track subject information throughout the registry. The Principal Investigator or authorized designee is responsible for the timely completion and electronic signature of all electronic case report forms. The information entered into the database will be checked systematically by the data management for inconsistent, illogical and/or missing data using electronic and manual validation checks defined

in the Data Validation Plan. If validation of data leads to discrepancies, data management will generate electronic queries. The timely resolution of the queries is under the responsibility of the monitor and the investigators at the Research Center. The query process is an ongoing process starting with the first data entered into the database. The electronic clinical data system used for this study has a security system that prevents unauthorized access to the data and any deletion of data (audit and edit trail).

9 Study Management

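### The adverse event outcome code *Resolved* covers both excluded and undetermined sequelae, so the outcome summary can overstate, and cannot understate, recovery without sequelae

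*Combined protocol and SAP*

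**What the plan says.** Section 6.2.5 asks that the recorded outcome reflect the event's status when it is recorded, and offers six codes. Three matter here.

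- *Resolved*: "The subject fully recovered from the event without any sequelae". The next sentence widens it: "This option also applies when it is unknown whether there are sequelae".
- *Resolved with sequelae*: "The subject's condition stabilized despite the persistence of sequelae".
- *Unknown*: "Knowledge of the current status of the AE/ADE is truly not available to the investigator". The example given is an event still ongoing when last observed, after which contact was lost. The entry closes with: "However, all efforts should be made to determine the outcome of any AE, especially that of an SAE/SADE".

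The outcome field feeds the safety analysis in Section 7.3: "Adverse events will also be summarized by relationship to the study device, implant procedure, by seriousness, severity and by outcome". No separate handling of undetermined sequelae is described there or elsewhere. Section 7.4.4 says: "No missing data will be imputed".

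**The concern.** A reader of an outcome table takes *Resolved* at its definition: the subject recovered and nothing was left behind. Under the added sentence, some of those entries may mean only that the event ended and nobody established whether it left anything. The table would give no way to tell the two apart.

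The distinction has some weight in this study. Table 3 lists expected effects for which residual damage is a main clinical question, among them temporary or permanent paresthesia, gum recession, and sinus or nasal fistula. Safety is a stated aim, and all analyses are descriptive, so the tables and listings are the safety analysis. A coding convention that can only move undetermined cases to the favourable side should at least be visible in them.

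The two meanings may also be hard to separate afterwards. Section 6.4 allows follow-up of an event to end once it is resolved. The short narratives required in Sections 6.2.1 to 6.2.3 concern seriousness and relationship; Section 6.2.5 asks for none on outcome.

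**Working it through.** The documents state no figure on this point, so there is none to reproduce. The check is a reading of the codes against one another, followed by a count.

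**Which code takes an event that has ended but whose sequelae were not determined?**

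1. *Resolved with sequelae* needs sequelae that are known to persist. It does not fit.
2. *Unknown* needs the current status to be unavailable. Here the status is known (the event ended); only the residue is unknown. It does not fit.
3. *Ongoing* and *Worsened* do not apply to an event that has ended, and *Fatal* is not in question.
4. *Resolved* takes it, by explicit instruction.

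**Effect on the count.** Among events that have ended, let:

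- K = events in which absence of sequelae was established;
- U = events in which sequelae were not determined;
- S = the number of those U events that do in fact have sequelae, so 0 ≤ S ≤ U.

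Then:

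- count shown as *Resolved* = K + U;
- confirmed full recoveries = K, so the excess is (K + U) − K = U;
- true full recoveries = K + (U − S), so the excess is (K + U) − (K + U − S) = S, which lies between 0 and U;
- the *Resolved with sequelae* row is short by the same S.

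Neither excess can be negative, so the rule works in one direction only. The documents give no value for U. As assumed values:

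| U (assumed) | Excess over confirmed full recoveries | Excess over true full recoveries |
|---|---|---|
| 0 | 0 | 0 |
| 1 | 1 | 0 to 1 |
| 2 | 2 | 0 to 2 |

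No percentage can be attached, because the number of events is not given either. The sample size ("This study size will enroll 20 subjects, 10 at each of the two Research Centers") counts subjects, and Section 7.3 does not say that every subject will contribute an event to the outcome table.

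**Set against Section 7.4.4.** That section is written mainly about drop-out before the primary endpoint, so it is not formally contradicted. Still, recording absence of sequelae where that information is missing acts like a favourable imputation and sits poorly beside a rule against imputing.

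**The case against.** The strongest reply is that U will be close to zero.

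- Adverse events are checked at each visit from surgery to 24 months after loading (Section 3.11.4 and the schedule) and are followed under Section 6.4. Section 6.2.5 itself asks for all efforts to establish the outcome.
- Bone at the study site is imaged repeatedly by periapical film and CBCT (Sections 3.11.8 and 3.11.9) and read centrally under blinding (Section 7.2). Losses above 2 mm in the first year after loading are flagged (Section 6.3.4). A reader might infer that residual bone defects would go unseen; the imaging plan does not support that as a typical case.
- Bone loss, recession, fistula and paresthesia are themselves listed adverse device effects. A symptom that has improved but not ended is *Ongoing*, so the sentence does not turn a partly recovered paresthesia into a *Resolved* one.
- Monitors pursue missing adverse event information (Section 9.3.2), and an independent committee adjudicates serious events (Section 6.4).

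All of this stands, and it limits the size. It does not remove the ambiguity: these provisions improve ascertainment, whereas the sentence governs what is recorded when ascertainment has failed. Sequelae that do not show on radiographs, and subjects who leave early, remain possible sources.

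It may also be said that a table footnote would disclose the convention. It would, but it would not tell the reader how many events are affected.

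**Conclusion.** The point holds as a minor one. As written, Section 6.2.5 lets the Section 7.3 outcome summary overstate recovery without sequelae: by exactly U against confirmed recoveries and by 0 to U against true recoveries. It cannot understate it through this rule. This assumes only that the codes are applied as worded. That U is probably small is a judgement from the visit and imaging schedule, not a figure in the documents.

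Stronger readings are not supported. A reader might infer that the table necessarily overstates full recovery, or that every event with undetermined sequelae is misclassified. Neither follows: such an event may truly have left nothing behind, and there may be no such event at all. Nor does the plan make a claim of no lasting harm; it plans only a summary by outcome. The primary endpoint and the incidence and severity of adverse events are unaffected.

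**What to change.** In Section 6.2.5, delete the sentence on unknown sequelae and reserve *Resolved* for events where absence of sequelae was established. Add a code *Resolved, sequelae not determined*, and show it as its own row in the Section 7.3 outcome table, so that U can be read directly.

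Do not route these events to *Unknown*. That would mix events known to have ended with events that were ongoing when contact was lost, and would discard information the investigator has.

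The cost is one extra case report form option and one table row, with a possibly slightly less favourable *Resolved* count. If events have already been coded under the present wording, those marked *Resolved* would need a check against source records.
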